7.3. Management of Intercurrent Events

7.3.1 Concomitant Medications

Patients will be removed from the protocol treatment if they initiate concomitant chemotherapeutic agents, corticosteroids, or other immunosuppressive agents, or other forms of immunotherapy. After meeting the inclusion criteria, all other medications deemed appropriate for the patient, by the investigator, may be administered to the patient. All medications and changes in medication during treatment will be recorded. Hormonal therapy and bisphosphonates may be continued in breast cancer patients if they have been stable on the agents for at least 1 month prior to enrollment.

7.3.2 Adverse Events

- 7.3.2.1 Toxicity will be graded according to the NCI Common Terminology Criteria for Adverse Events (CTCAE) version 4.0 (which can be downloaded from the CTEP web site (<http://ctep.cancer.gov>)). DLT is defined in Protocol Section 6.
- 7.3.2.2 Possible side effects from immunization may include local effects (pain, tenderness, redness or swelling), systemic effects (malaise, fatigue, myalgia, arthralgia, headache, nausea, vomiting, chills or fever), and allergic reactions such as hives, rash or anaphylactic reactions. Induction of auto-immunity, manifest as arthritis, serositis, nephritis, thyroiditis, colitis, neutropenia, etc., is theoretically possible, but has not been observed in our prior CEA vaccine studies. Also, liver function test abnormalities and liver failure are theoretically possible.

7.3.3 Treatment of Toxicity

For acute allergic reactions, use of diphenhydramine 25-50 mg IV, corticosteroids (Solumedrol 100 mg), and epinephrine (1:1000, 0.3-1 mL sq) should be considered. These medications are available in the clinical setting where the vaccine will be administered. For auto-immunity, corticosteroids (prednisone 0.5-1 mg/kg/d) should be considered. Clinical assessment of other targets, such as thyroid, arthritis, urticaria, or proteinuria, for auto-immunity and serum sickness like antigen-antibody complex disease, will also be performed as indicated.

7.3.4 Active Immunotherapy will be Discontinued for:

- 7.3.4.1 Life-threatening anaphylactic reactions related to active immunotherapy
- 7.3.4.2 DLT related to active immunotherapy
- 7.3.4.3 Disease progression (by RECIST criteria). Patients will be offered referral to a medical oncologist for discussion of other treatment options, and for continued medical care.
 - 7.3.4.3.1 Disease progression prior to completing the 3 study immunizations:

In the event that a patient undergoes reimaging studies prior to the completion of their 3 study immunizations and is found to have disease progression, they will be permitted to continue on the study as long as the progression has been 50% or less by RECIST criteria.

If a patient is removed from the study prior to completion of the assigned vaccine schedule for any reason other than toxicity, that patient will be replaced, in order to obtain data to help determine the toxicity of the immunizations. We will allow up to 3 replacements per cohort (Phase I, Dose levels 1 and 2; Phase II, MTD).

8. STATISTICAL CONSIDERATIONS

8.1. Safety

We will evaluate safety continuously in a cohort. We will make our overall assessment of whether to escalate to the next dose level at least 3 weeks after the last patient in the previous cohort has received their first injection. This decision will be made by the medical monitor and the Principal Investigator. A note will be generated following the assessment decision and filed in study binder. A dosage level will be considered safe if <33% patients treated at a dose level experience DLT (i.e., 0 of 3, ≤ 1 of 6, ≤ 3 of 12, or ≤ 5 of 18 patients). DLT is defined in Protocol Section 6. Safety will be evaluated in 3 or 6 patients at each dosage level in phase I. Safety will continue to be monitored among additional patients treated at the MTD in phase II. A patient will be considered evaluable for safety if treated with at least one immunization. DLTs will be observed through 9 weeks to accommodate safety evaluation of all 3 product doses.

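### Replaced early stoppers stay in the DLT denominator, so the rate-based 33% rules at the MTD can be diluted; the effect is modest and the plan should define a DLT-evaluable set

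*Combined protocol and SAP*

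**What the plan says.** References are to the most recent protocol version in the file, the one that adds Cohort 6.

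- **Who counts.** Section 8.1: "A patient will be considered evaluable for safety if treated with at least one immunization".
- **The rule.** Section 8.1: "A dosage level will be considered safe if <33% patients treated at a dose level experience DLT", with limits "0 of 3, ≤ 1 of 6, ≤ 3 of 12, or ≤ 5 of 18 patients".
- **The window.** Section 8.1: "DLTs will be observed through 9 weeks to accommodate safety evaluation of all 3 product doses". The escalation decision comes sooner, "at least 3 weeks after the last patient in the previous cohort has received their first injection".
- **Replacement.** Section 7.3.4, on patients removed before completing the schedule: "for any reason other than toxicity, that patient will be replaced, in order to obtain data to help determine the toxicity of the immunizations". The cap is "We will allow up to 3 replacements per cohort (Phase I, Dose levels 1 and 2; Phase II, MTD").
- **Where a rate decides.** Section 6 re-defines the MTD if the DLT rate in Cohort 4 or Cohort 5 reaches 33% at any point. The note under Cohort 4 applies the same threshold to everyone treated at the MTD in phases I and II together.
- **Where a count decides.** The section 6 instructions for cohorts 1, 2, 3 and 5 turn on having 0, 1 or 2 DLTs.

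No section says whether a replaced patient remains in the DLT denominator.

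**The concern.** The plan replaces a patient who leaves early without toxicity because that patient's toxicity information is incomplete. Under 8.1 the same patient is still fully evaluable. A patient who received one of three doses and left DLT-free is therefore a complete non-event in a rate meant to describe nine weeks and three doses, and the replacement is added on top. The <33% verdict and the combined MTD rule are primary safety decisions. Extra non-events lower the rate without adding evidence about doses 2 and 3.

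**Working it through.** **1. The plan's own limits.** The largest x with x/n < 0.33 for n = 3, 6, 12, 18 is 0, 1, 3, 5. This matches section 8.1.

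**2. Enlarged denominators.** The same rule gives at most 4 for n = 13 to 15 and at most 6 for n = 19 to 21. So 4/12 = 33.3% fails but 4/13 = 30.8% passes. Likewise 6/18 = 33.3% fails, while 6/19 = 31.6% and 6/21 = 28.6% pass.

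**3. Risk model.** The documents give no per-dose DLT risk. Let P be the three-dose risk and q the risk for a one-dose patient. With equal risk per dose, q = 1 − (1 − P)^(1/3), which is 0.125 at P = 0.33 and 0.157 at P = 0.40. The range shown runs from q = P (all risk at dose 1) to q = 0.

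**4. A single final look.** This takes 18 full-course patients (limit 5), then adds three one-dose patients (n = 21, limit 6), by exact binomial convolution.

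| P | 18 only | 18 + 3, equal risk | range, q = P to q = 0 |
|---|---|---|---|
| 33% | 42.4% | 54.7% | 43.1% to 62.0% |
| 40% | 20.9% | 30.0% | 20.0% to 37.4% |

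**5. The path section 6 describes.** Cohort 3 must show 0 or 1 DLT in six. The combined rate is then checked after each phase II patient, stopping at ≥33%. Three one-dose drop-outs are placed at random in phase II (simulation, 400,000 runs per setting).

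| P | no drop-outs | 3 drop-outs, equal risk | range, q = P to q = 0 |
|---|---|---|---|
| 33% | about 20% | about 23% | about 19% to 25% |
| 40% | about 9% | about 10% | about 7% to 12% |

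**6. Count rules.** With a fixed limit of 1 DLT, six patients at P = 33% pass with probability 35.8%. Three extra one-dose patients (equal risk) lower this to 26.6%, so a count limit becomes stricter.

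**7. Bias of each denominator.** Take P = 0.33 and equal risk, and let a fraction d of DLT-free patients leave after dose 1 (assumption). The risk over doses 2 and 3 is 1 − 0.875² = 0.234.

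- All treated: 0.125 + 0.875(1 − d)(0.234), which is 30.9% at d = 10% and 28.9% at d = 20%.
- DLT, or complete and DLT-free: the same numerator divided by itself plus 0.67(1 − d). At d = 10% this is 0.309/(0.309 + 0.603) = 33.9%; at d = 20% it is 0.289/(0.289 + 0.536) = 35.0%.

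Against a true 33%, all-treated is low by about 2 to 4 points. The evaluable set is high by about 1 to 2.

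**8. Rules against each other.** In cohort 2 expanded to six, with one replaced DLT-free stopper added, 2 DLTs give 2/7 = 28.6%. The general rate rule in section 6 would allow progression; the cohort 2 count instruction would not.

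**The case against.** Several points on the other side stand.

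- A reader might take the single-look figures (42% to 55%, 21% to 30%) as the size of the problem. They are not. Section 6 has the cohort 3 gate and repeated checks first, and the 6/18 against 6/21 flip needs an accrual order in which no earlier look reaches 33%.
- A reader might infer that dose escalation itself is loosened, or that the error always runs in the unsafe direction. The cohort 1, 2, 3 and 5 instructions are counts. Escalation through cohort 3 uses the visit at least 3 weeks after dose 1, so a one-dose patient who attends it is fully observed for that decision. If DLT risk sits at dose 1, passing becomes slightly less likely.
- One-dose patients are not unobserved. Section 10.5 follows AEs to 30 days after the last dose, and section 7.1 evaluates discontinued patients who received any treatment. That covers the dose given, but not the doses missed.
- The double counting is inferred. The summary and section 4.3 speak of evaluable patients plus replacements, which can be read as the replacement taking the slot, and 8.1 gives no limit for 19 to 21. That reading conflicts with the 8.1 definition, so the silence still needs resolving.
- Early drop-out has no stated frequency. Section 7.3.4 limits it by letting patients with progression of 50% or less continue, and dose level 3 is not on the replacement list. The exposure is mainly Cohort 4.

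Requiring three doses and Week 9 for every use of the 33% rule would also fail, because no DLT-free patient would be evaluable at the 3-week escalation decision.

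**Conclusion.** The point holds for the 9-week <33% verdict and the combined MTD rate rule. As written, DLT-free early stoppers and their replacements both enter the denominator, and a 33.3% result can become a passing one. Under the section 6 decision path with three drop-outs and equal risk per dose, the chance of passing rises by roughly 2 to 3 percentage points at a true risk of 33%, and by less than 2 at 40%. Over the full range of one-dose risk the change can be a small fall or a rise of about 5 points. The result rests on the assumed per-dose risk, on three drop-outs placed at random in phase II, and on checking the combined rate; the sentence applying 33% to Cohort 4 alone was not modelled. The documents do not support a claim that the count-based escalation steps are weakened, or that early drop-out is common. This is a gap in definition worth closing, and not a failure of the design.

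**What to change.** Change wording in 8.1 and leave the thresholds alone.

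1. Keep at least one immunization as the population for AE tables and listings.
2. For rate-based rules, define a DLT-evaluable set: patients with a DLT, plus DLT-free patients who completed the window for that decision. The window is the visit at least 3 weeks after the first dose for escalation, and all three immunizations with Week 9 for the 9-week and MTD rates.
3. State that replaced DLT-free patients are outside that denominator.
4. Report the all-treated rate alongside.

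The cost is the upward bias in step 7 of the working: early stoppers are kept only when they had a DLT. It is about half the size of the present downward bias in those scenarios, and reporting both rates brackets it. With continuous monitoring, the evaluable denominator also lags enrolment, so the text should say how patients still in their window are handled.

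Reconcile at the same time:

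- The rate and count rules in section 6.
- The replacement text in 7.3.4. Three replacements in each of three listed cohorts make 9, against the 12 planned.
- The current Table 3. Its entries 1, 2, 4, 8, 10, 13 track about 33% of cumulative enrolment (3, 6, 12, 24, 30, 40) instead of each dose level. It shows 8 for Cohort 4 with n = 12, where 8.1 allows at most 3 of 12.

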8.2. Rate of Immune Response

Immune responses against CEA will be evaluated from the peripheral blood of patients from among the following studies at the discretion of the Principal Investigator (ELISpot, cytokine flow cytometry, and antibody responses). We will determine the percentage of patients with a positive immune response. We define a positive immune response by ELISpot as described at the 2002 Society of Biologic Therapy Workshop on “Immunologic Monitoring of Cancer Vaccine Therapy”, i.e. a T cell response is considered positive if the mean number of spots adjusted for background in six wells with antigen exceeds the number of spots in six control wells by 10 and the difference between single values of the six wells containing antigen and the six control wells is statistically significant at a level of $p \leq 0.05$ using the Student’s t test. Immunogenicity assays will occur prior to each immunization and at week 9. Immune response will be assessed among the 18 patients treated at the MTD (12 in phase I and 12 in Phase II). The therapy will be considered of further interest if 9 of 18 patients treated at the MTD dose exhibit an immune response as defined above. Meeting this criterion establishes that the immune response rate is at least 33% with approximately 90% confidence. At significance level 0.1 there is 82% power to test the null hypothesis that the immune response rate is ≤ 0.33 versus the alternative that the immune response rate is ≥ 0.58 . The magnitude of response will also be described. A patient will be considered evaluable for immune response if they receive at least 3 immunizations.

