Statistical Analysis	
Safety: We will evaluate safety in each cohort at least 3 weeks after the last patient in the previous cohort has received their first injection. A dosing scheme will be considered safe if <33% of patients treated at a dosage level experience DLT (e.g., 0 of 3, ≤1 of 6, ≤3 of 12 or ≤5 of 18 patients). A patient will be considered evaluable for safety if treated with at least one immunization.
 
Rate of immune response: We will determine the percentage of patients with a positive immune response. We define a positive immune response by ELISpot as described at the 2002 Society of Biologic Therapy Workshop on “Immunologic Monitoring of Cancer Vaccine Therapy”, i.e. a T cell response is considered positive if the mean number of spots in six wells with antigen exceeds the number of spots in six control wells by 10 and the difference between single values of the six wells containing antigen and the six control wells is statistically significant at a level of $p \leq 0.05$ using the Student’s t test. Immunogenicity assays will occur prior to each immunization and at week 9. Immune response will be assessed at the MTD. An observed immune response in 9 of 18 patients will be considered sufficient evidence of immune response to justify further investigation. Meeting this criterion establishes that the immune response rate is at least 33% with approximately 90% confidence. The magnitude of response will also be described. A patient will be considered evaluable for immune response if they receive at least 3 immunizations.

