- 6) Cohort 6: Up to ten (10) patients will receive Ad5 [E1-, E2b-]-CEA(6D) at a dose of 5×10^{11} particles SQ in 1.0 mL every 3 weeks for 3 immunizations. Patients will be permitted to receive booster doses of Ad5 [E1-, E2b-]-CEA(6D) every 3 months for a period of two years following the first 3 treatments. In the event that a qualified patient undergoes reimaging prior to the completion of their initial 3 study immunizations and is found to have disease progression, the patient should continue on the immunization protocol because this could be a “flare reaction” associated with the vaccine which may be an inflammatory response. Patients will be required to have MRI/CT scans performed prior to initiation of treatment, at 3 month intervals +/- 1 month for 12 months or if the investigator believes signs or symptoms are suggestive of progression or relapse. All patients will be followed for overall survival for a period of 24 months from initiation of treatment.
- 7) Patients will have 90 mL peripheral blood drawn prior to each immunization and approximately 3 weeks after the third immunization (Week 9) to determine whether there is an effect on the immune response at specific time points during the study and/or after a specific number of immunizations.
- 8) Time to progression will be measured using CT scans performed at approximately 3 month intervals (based on clinical standard of care).
- 9) For all patients, if scheduling conflicts arise, the scheduled 3-week interval between immunizations may be modified so that the interval between immunizations is between 20 and 28 days (3 weeks -1 day to 3 weeks +7 days). If the second and/or third immunization is delayed, the subsequent immunizations should occur no earlier than 20 days after the previous immunization.
- 10) The following safety events will trigger a temporary suspension of study vaccinations:
 - a) If one or more patients develop a Grade 4 allergic reaction without a clear attributable cause, other than study vaccine
 - b) Death not attributed to disease.

Assessment of these halting rules is a review of cumulative events for all study participants, and should not be confused with reasons for delaying or terminating the immunization schedule of any individual patient.

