7.1.4 Immunological Assessment

Weeks 0, 3, 6, and 9:

Peripheral blood (90mL) will be drawn prior to each immunization and approximately 3 weeks after the last immunization to determine whether there is an effect on the immune response at specific time points during the study and/or after a specific number of immunizations. Peripheral blood mononuclear cells (PBMC) will be assayed for T cell responses to CEA using ELISPOT at all time points, plus proliferation assays, multi-parameter flow cytometric analysis, and cytotoxicity assays, if possible and at the discretion of the investigator. Serum from each blood draw will be archived and sent to Etubics Corporation for Ad5 neutralizing level determination.

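### The ELISpot responder rule has no week-0 comparison and names no deciding sample, so patients already CEA-reactive before dose 1 can count toward the 9 of 18

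*Combined protocol and SAP*

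**What the plan says.** The current text is the last protocol version in the file, the one with Cohort 6. Section 8.2, Rate of Immune Response, sets two conditions for a positive T cell response. The first is that "the mean number of spots adjusted for background in six wells with antigen exceeds the number of spots in six control wells by 10". The second is a Student's t test between the six antigen wells and the six control wells at p ≤ 0.05. The Statistical Analysis row of the Protocol Summary repeats the rule without the background adjustment: "if the mean number of spots in six wells with antigen exceeds the number of spots in six control wells by 10".

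On timing, Section 8.2 says: "Immunogenicity assays will occur prior to each immunization and at week 9". It does not say which of these samples, or how many, make a patient a responder. A patient is evaluable after at least 3 immunizations, and there is no baseline condition. The therapy is of further interest if 9 of 18 patients at the MTD respond, and "Meeting this criterion establishes that the immune response rate is at least 33% with approximately 90% confidence". The test is of ≤ 0.33 against ≥ 0.58 at level 0.1, with 82% power. The same section opens by letting immune response be evaluated "from among the following studies at the discretion of the Principal Investigator" (ELISpot, cytokine flow cytometry, antibody).

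Section 7.1.4 covers weeks 0, 3, 6 and 9 and says that PBMC "will be assayed for T cell responses to CEA using ELISPOT at all time points". Section 2 states the secondary objective as CEA-specific immune response to the immunizations. Eligibility criterion 4.1.9 admits patients whose earlier CEA-targeted immunotherapy stopped at least 3 months before enrollment.

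**The concern.** The objective is a response caused by the vaccine. The rule detects CEA-reactive T cells in a sample, whatever their origin. A patient who was reactive at week 0 and is unchanged afterwards has shown no induced response but satisfies the definition. Criterion 4.1.9 means such patients are not excluded at entry.

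The 9-of-18 rule is the plan's only stated criterion for further interest. If it counts pre-existing reactivity, the claim attached to it (a rate of at least 33%) is about a different quantity from the one in the objective. Read literally, the rule does not exclude even the pre-dose-1 assay as the deciding one.

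**Working it through.** **Inputs from the documents:** n = 18, pass mark 9, p0 = 0.33, p1 = 0.58, level 0.1, power 82% (Section 8.2). **Assumed, because the visible text gives no value:** the share of patients positive at week 0 (5%, 10%, 20%), and the induction rate in the others.

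**1. The plan's own figures.** With X ~ Bin(18, p), P(X ≥ 9) is 0.102 at p = 0.33 and 0.823 at p = 0.58. The one-sided 90% Clopper-Pearson lower bound for 9/18 is 0.329. These agree with the stated level, power and confidence. The binomial arithmetic is sound; the question is what is counted as a response.

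**2. What nine observed responders would show.** If some of the nine were already positive at week 0, the bound for newly induced response uses only the remainder out of 18. No prevalence has to be assumed.

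| Already positive at week 0 | Newly induced | One-sided 90% lower bound |
|---|---|---|
| 0 | 9/18 | 0.329 |
| 1 | 8/18 | 0.279 |
| 2 | 7/18 | 0.231 |
| 3 | 6/18 | 0.185 |

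**3. Chance of passing under the rule as written.** Let s be the share positive at week 0 and still positive at the deciding sample, and t the induction rate in everyone else. The counted rate is s + (1 − s)t. For example, s = 0.10 and t = 0.33 give 0.10 + 0.90 × 0.33 = 0.397.

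| s | t = 0.33: rate, P(≥ 9/18) | t = 0.20: rate, P(≥ 9/18) | t = 0: P(≥ 9/18) |
|---|---|---|---|
| 5% | 0.364, 0.17 | 0.24, 0.015 | below 0.001 |
| 10% | 0.397, 0.25 | 0.28, 0.039 | below 0.001 |
| 20% | 0.464, 0.47 | 0.36, 0.160 | 0.004 |

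With s = 0 the t = 0.33 column is the design value, 0.10. Solving for s at t = 0.33, the pass chance reaches 0.15, 0.20 or 0.30 at s = 3.8%, 7.0% or 12.3%.

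**4. Effect of excluding week-0 positives.** Suppose a responder must be positive at week 9 and not at week 0, and week-0 positives (share b) stay in the 18 as non-responders. The counted rate is then (1 − b)t.

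| b | t = 0.58: rate, power | t = 0.33: rate, P(≥ 9/18) |
|---|---|---|
| 5% | 0.551, 0.75 | 0.3135, 0.077 |
| 10% | 0.522, 0.66 | 0.297, 0.056 |
| 20% | 0.464, 0.47 | 0.264, 0.027 |

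**The case against.** Several points can be made for the plan.

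- **Timing is half implied.** Evaluability needs 3 immunizations, and week 9 is the only sample in the primary schedule after the third. That makes a week-9 reading likely, but it is not written down. It would settle timing only; a patient positive at both week 0 and week 9 would still count.
- **Comparison over time is intended.** Section 7.1.4 says the blood is drawn "to determine whether there is an effect on the immune response at specific time points". This states a purpose for sampling and does not enter the definition that the 9-of-18 rule applies. It does mean that the week-0 data will exist.
- **The background adjustment might mean baseline.** The term is undefined, sits in a comparison with control wells, and is missing from the Protocol Summary.
- **The cited 2002 workshop might require a baseline.** That source is not available here. The protocol spells out the operative rule itself, and that wording has no week-0 term.
- **Week-0 positivity may be rare, and the consequence is limited.** Both are fair. The visible text gives no rate and the background section is redacted. The objective is secondary, and no dose, cohort or stopping rule in Section 6 depends on 9 of 18.

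A reader might infer more than the documents support in two ways. One is that an inert or weakly active vaccine would readily pass. With no effect the chance is at most 0.004 for shares up to 20%. At 20% induction it exceeds the design 0.10 only at the 20% share, where it is 0.160. The other is that accepting positivity at any of several samples would by itself break the 10% error. It would not: at a true rate of 0.33 for whatever is defined as response, the error is still 0.102. More samples change what is being estimated, not the error of the test.

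**Conclusion.** The point holds as a defect in the endpoint definition. Followed exactly, Section 8.2 and the Protocol Summary measure ELISpot positivity at an unspecified sample, and the confidence statement applies to that quantity. The plan's alpha, power and confidence are correct for the quantity it counts.

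The lower bounds in step 2 rest only on how many of nine responders were positive beforehand; one such patient takes the bound clearly below 33%. The pass probabilities rest on assumed week-0 shares, on those patients staying positive, and on an assumed induction rate in the rest, so they are illustrations rather than estimates. The inflation is material near the null boundary of 33% induction and small well below it. The wording should be corrected, because this is the only go-forward criterion and the samples needed are already scheduled.

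**What to change.** In Section 8.2 and the Protocol Summary:

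1. Name week 9 as the deciding ELISpot sample. It is already scheduled and follows all 3 immunizations.
2. Add a week-0 condition. The simplest version is that a responder meets the criterion at week 9 and did not meet it at week 0. Week-0 positives stay in the 18, do not count as responders, and are listed separately with their change from week 0. A prespecified rise over week 0 would also close the gap and would let boosted patients count. Either is acceptable if fixed in advance.
3. State that ELISpot decides the 9-of-18 rule, whatever other assays the Principal Investigator selects.
4. Use the same spot formula in both places, with the background adjustment either defined or removed.

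Cost: wording only, since week-0 and week-9 ELISpot are already required by Section 7.1.4. The simplest version has a statistical price. At week-0 rates of 5%, 10% or 20%, power falls from 0.82 to 0.75, 0.66 or 0.47, and the rule becomes conservative at 33% induction in week-0 negatives (pass chance 0.077, 0.056 or 0.027). If the sponsor expects week-0 positivity to be common, that is a reason to consider the rise-over-week-0 version.
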